#### 11.1.4 Duration of Response

Duration of overall response: The duration of overall response is measured from the time measurement criteria are met for CR or PR (whichever is first recorded) until the first date that recurrent or progressive disease is objectively documented (taking as reference for progressive disease the smallest measurements recorded since the treatment started, or death due to any cause. Participants without events reported are censored at the last disease evaluation).

Duration of overall complete response: The duration of overall CR is measured from the time measurement criteria are first met for CR until the first date that progressive disease is objectively documented, or death due to any cause. Participants without events reported are censored at the last disease evaluation.

Duration of stable disease: Stable disease is measured from the start of the treatment until the criteria for progression are met, taking as reference the smallest measurements recorded since the treatment started, including the baseline measurements.

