### **13.5 Analysis of Secondary Endpoints**

#### Efficacy Endpoints

All patients who initiated protocol therapy will be evaluated for PFS per irRECIST criteria, ORR, CBR, and OS. ORR and CBR will be evaluated using RECIST 1.1 and irRECIST criteria (as defined in Section 11.3). DOR will be evaluated among patients who had CR or PR. All these endpoints will be estimated separately in the two treatment arms.

The objective response rate (CR + PR) and immune-related response rate (irCR + irPR) will be reported by arm with 90% exact confidence intervals. Objective response rate and immune-related response rate will be compared between Arm A and Arm B, respectively using a Pearson

chi-squared test for difference in proportions with a one-sided  $\alpha$  of 0.1.

Clinical benefit is defined as CR, PR or SD  $\geq$  27 weeks. Clinical benefit will be calculated using RECIST 1.1 and irRECIST criteria, respectively. Clinical benefit rate (CR+PR+SD $\geq$ 27 wks) per RECIST 1.1 and irRECIST criteria will be reported respectively with 95% exact confidence intervals. CBR will be compared between two treatment arms using a Pearson chi-squared test for difference in proportions with a one-sided  $\alpha$  of 0.1.

PFS per irRECIST and OS will be also analyzed using Kaplan-Meier product-limit estimates and 95% confidence bands. PFS per irRECIST is defined as the time from study randomization to disease progression per irRECIST or death due to any cause, whichever occurred first. Patients alive without disease progression per irRECIST are censored at the date of last disease evaluation. OS is defined as the time from study randomization to death due to any cause. Patients will be censored at the date they were last known alive. The hazard ratio for each time-to-event endpoint will be estimated with 95% confidence intervals derived from the Cox proportional hazard model, but no hypothesis testing will be conducted.

DOOR is defined as the time from CR or PR achieved until renewed disease progression is detected. DOOR will be calculated per RECIST 1.1 and irRECIST criteria, respectively, and descriptive statistics will be used to summarize the intervals observed by arm.

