In the group of patients treated with Pembrolizumab after progression on eribulin mesylate, CBR, PFS, OS, and DOOR after they received Pembrolizumab will be estimated using binomial, Kaplan-Meier and descriptive statistics, respectively with 95% confidence intervals. For this group, PFS and OS will start from the time of initiating Pembrolizumab. Under an assumption that approximately two-thirds of patients elect to cross over (n=30), the maximum width to an exact confidence interval for a proportion will be 0.374.

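### Section 13.5 gives duration of response no death event and no censoring rule, in conflict with 11.1.4 for RECIST 1.1 and leaving a gap for irRECIST; without censoring the reported durations tend to be too short

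*Combined protocol and SAP*

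**What the plan says.** Duration of response (DOR, written DOOR in parts of 13.5) is defined twice in the combined protocol and SAP.

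- **Section 11.1.4**, under the RECIST 1.1 criteria, runs from first CR or PR "until the first date that recurrent or progressive disease is objectively documented", with the end of the rule reading "or death due to any cause. Participants without events reported are censored at the last disease evaluation".
- **Section 13.5, efficacy endpoints:** "DOOR is defined as the time from CR or PR achieved until renewed disease progression is detected". It is calculated under both RECIST 1.1 and irRECIST, and "descriptive statistics will be used to summarize the intervals observed by arm". The definition does not refer back to 11.1.4.

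The paragraph of 13.5 just before this one treats the other time-to-event endpoints differently: "PFS per irRECIST and OS will be also analyzed using Kaplan-Meier product-limit estimates". It also gives a censoring rule for each of them. For patients who cross over to pembrolizumab, "CBR, PFS, OS, and DOOR after they received Pembrolizumab will be estimated using binomial, Kaplan-Meier and descriptive statistics", paired in order. That assigns Kaplan-Meier to PFS and OS and descriptive statistics to duration of response.

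**The concern.** A responder who dies without progression has an event under 11.1.4 and no defined end under 13.5. A responder still in response at the cutoff is censored under 11.1.4 and has no stated treatment under 13.5. An analyst working from 13.5 must either leave ongoing responses out or enter them at their length so far. Both choices ignore censoring and can pull the summary down.

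The pull grows with the true duration, because more of the long responses are unfinished at the cutoff. A difference between arms in durability, which is where a benefit of adding pembrolizumab might show, would be compressed. Two definitions in one document also leave a choice to be made after the data are seen, in an open-label trial.

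**Working it through.** The documents give no numerical assumption for DOR, so there is no plan figure for it to reproduce. The timetable used below is the plan's own. With 4.1 vs 7.1 months, 18 months of accrual, 6 of follow-up and 5% dropout at 1 year, I get 69.9 expected PFS events against the planned 70. Month 24 is therefore a fair base case. The stated 83% power also reproduces (84.1% ignoring the futility look, 82.6% with it) and does not depend on DOR.

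**Inputs**
- Accrual 18 months, follow-up 6 months: 13.2. Alternative follow-up of 12 months: the other final-analysis trigger in 13.4.
- Background median DOR for eribulin, 5.6 and 4.1 months: the two phase II studies in 2.4.
- Response at the first 9-week scan, about 2.1 months: scan interval from Section 10, timing assumed.
- Exponential durations: assumed.
- True medians of 9 and 12 months: assumed, to show what happens with durable responses.
- Dropout is left out of the main table and added as a check.

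**Formulas.** Let λ = ln 2 / median. Time available after response, C, is uniform from 6 − 2.1 = 3.9 to 24 − 2.1 = 21.9 months.
- Share ongoing at cutoff: p = (e^(−3.9λ) − e^(−21.9λ)) / (18λ).
- Reading A, completed intervals only: the median t solves P(T ≤ t and T ≤ C) / (1 − p) = 0.5.
- Reading B, ongoing intervals counted as complete: the median t solves e^(−λt) × P(C > t) = 0.5.

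**Worked case, true median 5.6 months.** λ = 0.6931/5.6 = 0.1238.
- p = (0.617 − 0.0665)/2.228 = 0.247.
- Reading A: for t below 3.9, (1 − e^(−λt))/0.753 = 0.5, so e^(−λt) = 0.6235 and t = 3.8.
- Reading B: at t = 5.06, e^(−λt) = 0.5345 and P(C > t) = (21.9 − 5.06)/18 = 0.9356. The product is 0.500, so t is about 5.1.

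**Results at 18+6 months**

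| True median (months) | Ongoing | Reading A | Reading B |
|---|---|---|---|
| 4.1 | 16% | 3.2 | 4.05 |
| 5.6 | 25% | 3.8 | 5.1 |
| 9 (assumed) | 40% | 4.6 | 6.8 |
| 12 (assumed) | 50% | 5.1 | 7.8 |

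A true contrast of 5.6 vs 12 months (difference 6.4) would appear as 3.8 vs 5.1 (difference 1.3) under A, or 5.1 vs 7.8 (difference 2.7) under B.

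**At 18+12 months**, C runs from 9.9 to 27.9. True medians of 4.1 and 5.6 read 3.8 and 4.7 under A. Under B they are unbiased, because no response can be cut off before 9.9 months.

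**Check with dropout.** A simulation adding 5% dropout a year at 18+6 months moves reading A by at most 0.1 month and gives 4.0, 4.9, 6.6 and 7.5 under B. Kaplan-Meier with the 11.1.4 rule returns 4.1, 5.6, 9.0 and 12.0, the assumed true medians.

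**Death taken separately.** If Kaplan-Meier were used but deaths were censored, and 10% to 20% of events were deaths (assumed), a true median of 5.6 would read 6.2 to 7.0. Omitting death does not shorten duration, and in this form it lengthens it.

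**Number of responders.** At the 11.0% response rate quoted for eribulin in 2.4, 0.11 × 44 = 4.84, or about 5 in the eribulin arm.

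**The case against.** The strongest reply is that 13.5 does not say that ongoing responses are dropped. It speaks of the intervals observed, and 11.1.4 supplies a censoring rule that 13.5 does not revoke. A reader might infer a declared plan to summarise completed responses only, and the documents do not support that. What they do show is a method left open and inconsistent between sections, so the size of the bias has to be given across both readings. This part stands.

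The size also depends on the cutoff. At the documents' own eribulin medians, reading B loses only about 0.05 and 0.5 months at 18+6, and nothing at 18+12. The larger losses need either reading A or durations of 9 to 12 months, which are assumptions. This stands too.

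Finally, DOR carries no hypothesis test and responders will be few. With 5 responders and a true median of 5.6 months, the 10th to 90th percentile range of a Kaplan-Meier median is about 2.3 to 14 months. With a true median of 12 the median is not reached in about 35% of trials. Listing individual durations would be informative at this size. That limits the weight of the point but does not justify omitting censoring. Kaplan-Meier with counts of events and censored responses shows the uncertainty, while a median of uncensored intervals hides it.

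The objection does not remove the conflict itself. Kaplan-Meier is named for PFS and OS in the same section and withheld from duration of response twice, the second time in the crossover paragraph.

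**Conclusion.** The concern holds as a conflict between 13.5 and 11.1.4 for RECIST 1.1 and as a missing rule for irRECIST. A reader might call both parts a contradiction, but 11.1.4 sits under the RECIST 1.1 criteria, so there is no second irRECIST definition to contradict.

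Missing censoring biases the reported duration short when enough responses are ongoing at the cutoff, and more so for longer responses. At 18+6 months the background eribulin medians lose about 0.9 and 1.8 months under reading A, or about 0.05 and 0.5 under reading B. The assumed medians of 9 and 12 months lose 4.4 and 6.9, or 2.2 and 4.2. These figures rest on exponential durations, response at 9 weeks and large samples. A reader might also infer that leaving out death adds to the shortening. It does not; it is a separate inconsistency.

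The effect is on a secondary descriptive estimate. The primary PFS comparison and its power are unaffected. The wording should be corrected before analysis.

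**What to change.** In 13.5, replace the definition with the 11.1.4 rule and apply it to RECIST 1.1, irRECIST and the crossover group: from first CR or PR to progression by the relevant criteria or death from any cause, with ongoing responses censored at the last disease evaluation. Replace descriptive statistics with Kaplan-Meier medians and 95% confidence intervals by arm, and report the numbers of events and of censored responses. A listing of individual durations can be added, given the small numbers.

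The cost is SAP wording. Progression, death and last-evaluation dates are already needed for PFS. The downside is that with about 5 responders in an arm the median may not be reached or may have a wide interval, which is an accurate picture of what the trial can say about duration.

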### Safety and tolerability

All patients will be evaluable for toxicity from the time of their first treatment with any study agent. Toxicity will be graded according to NCI CTCAE, Version 4.0. Toxicities will be summarized by maximum grade and by treatment arm. Incidence rate of each toxicity will be reported with 95% exact CI. The incidence rates of any grade 3+ toxicity will be compared between two arms using a Pearson chi-squared test for difference in proportions with a one-sided  $\alpha$  of 0.1..

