#### *Pivotal Phase III trial*

In the phase III EMBRACE trial, AEs occurred in 99% of patients receiving eribulin mesylate, however serious AEs occurred in 25% and AEs leading to therapy discontinuation occurred in 13% of patients on study. The primary toxicities with eribulin mesylate were asthenia or fatigue (54%) neutropenia (52%). Grade 4 neutropenia lasting more than 1 week occurred in 12% of patients and F+N occurred at low incidence (5%). Patients with elevated ALT/AST or bilirubin experienced a higher frequency of grade 4 neutropenia or F+N. Peripheral neuropathy was the most common AE leading to discontinuation of therapy, occurring in 5% of patients. Neuropathy lasting more than one year occurred in 5% of the patients. Alopecia occurred in 45% of patients. Nausea occurred in 35% of patients, but it was grade 3 just in 1% of patients. Diarrhea occurred in 18% of cases; in all cases was grade 1 or 2. Dose interruptions, delays and reductions were undertaken in 6%, 49% and 29% in the eribulin mesylate group, respectively.

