## 7.8 Routine Adverse Event Reporting

All Grade 2 or greater Adverse Events **must** be reported in routine study data submissions to the Overall PI on the toxicity case report forms. **AEs reported through expedited processes (e.g., reported to the IRB, FDA, etc.) must also be reported in routine study data submissions.**

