### 13.7.2 Evaluation of Safety

The safety population will be used in the safety data summaries. The safety population consists of all patients who took at least one dose of any randomized treatment and who have at least one post-baseline safety assessment. Note that a patient who had no adverse events constitutes a safety assessment. Patients who have received at least one dose of study drug but have no post-treatment safety data of any kind would be excluded.

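### Section 13.5 reports toxicity incidence with no grade floor, but Section 7.8 requires only grade 2 or greater events on the forms, so any-grade rates are understated if sites record the minimum

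*Combined protocol and SAP*

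**What the plan says.** The analysis rule is in Section 13.5, under Safety and tolerability. It has two descriptive parts: "Toxicities will be summarized by maximum grade and by treatment arm. Incidence rate of each toxicity will be reported with 95% exact CI". Neither carries a grade limit. The sentence after them sets up the only formal safety comparison, a chi-squared test between arms, and restricts it explicitly to grade 3+.

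The data rule is in Section 7.8. It applies to "All Grade 2 or greater Adverse Events", which must "be reported in routine study data submissions to the Overall PI on the toxicity case report forms". It adds one further route onto the forms: "AEs reported through expedited processes (e.g., reported to the IRB, FDA, etc.) must also be reported in routine study data submissions". No grade is attached to that second route.

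Section 13.7.2 defines the safety population and keeps a patient with no adverse events in it.

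**The concern.** The two rules use different thresholds for what counts as an event. The forms are only required to hold grade 2 or greater events, while the tables are described as covering every toxicity at every grade. For a given toxicity, a patient with no event and a patient whose worst event was grade 1 can look the same on the forms.

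Safety and tolerability of the combination is a secondary objective (Section 1.3.7). Section 7.1.2 says most adverse events with eribulin are grade 1 or 2, so the part of the distribution that need not be recorded may not be small. An unlabelled incidence table would probably be read as any-grade. An exact confidence interval around it would not help, because it reflects sampling error in what was recorded and not events that were never required to be recorded.

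**Working it through.** **Inputs**

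- Recording floor: grade 2 or greater, plus expedited events (Section 7.8).
- Reporting floor: none stated for incidence or for the maximum-grade summary (Section 13.5).
- Patients per arm: 44 (Section 13.2). Section 4.1 replaces randomized patients who never start treatment, so 44 treated per arm is a reasonable working figure.
- Example values of p, the any-grade incidence: 18% for diarrhea and 54% for asthenia or fatigue, both from the account of the phase III eribulin trial in Section 2.4. They serve only as convenient starting values.
- g, the share of affected patients whose maximum grade is 1: not in the documents. Section 7.1.2 pools grades 1 and 2, and so does the phase III account ("Diarrhea occurred in 18% of cases; in all cases was grade 1 or 2"). Every value of g below is an assumption.

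**Step 1. Does another section require grade 1 events to be recorded?** Sections 7.3 to 7.7 deal with serious events, events of clinical interest, overdose and pregnancy. Section 7.7 also promises non-serious events to the eribulin supplier in the final report, but it sets no recording rule. The Section 10 calendar has a row for adverse event evaluation with no grade rule. None of these requires routine recording of a non-serious grade 1 event.

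**Step 2. Does Section 13.5 mean any grade?** It names a floor where it wants one, in the grade 3+ test. The incidence sentence just before has none, so any-grade is its plain reading.

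**Step 3. Mechanism.** Under minimum recording, a patient with maximum grade 1 for a toxicity is in the denominator and not in the numerator:

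reported incidence = p(1−g), shortfall = pg.

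If a share v of those patients has the grade 1 event volunteered, reported incidence = p(1−g(1−v)), which lies between p(1−g) and p. It then depends on site habit as well as on the drugs.

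**Step 4. Illustration.** The plan states no toxicity rate that could be reproduced. As a check on the exact-interval calculation, Section 13.5 gives a maximum 95% width of 0.374 for n = 30; Clopper-Pearson gives 0.3741, which agrees. With n = 44, counts rounded to whole patients:

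| g (assumed) | p = 18%: p(1−g) | Recorded (95% exact CI) | p = 54%: p(1−g) | Recorded (95% exact CI) |
|---|---|---|---|---|
| 0 | 18.0% | 8/44 = 18.2% (8.2–32.7) | 54.0% | 24/44 = 54.5% (38.8–69.6) |
| 25% | 13.5% | 6/44 = 13.6% (5.2–27.4) | 40.5% | 18/44 = 40.9% (26.3–56.8) |
| 50% | 9.0% | 4/44 = 9.1% (2.5–21.7) | 27.0% | 12/44 = 27.3% (15.0–42.8) |
| 75% | 4.5% | 2/44 = 4.5% (0.6–15.5) | 13.5% | 6/44 = 13.6% (5.2–27.4) |

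The relative loss is g whatever the value of p. At g = 75% the interval for the 18% event ends at 15.5%, below the true rate. For the 54% event the interval already misses the true rate at g = 50%.

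**Step 5. What does not move.** Grade 2+ and grade 3+ incidence contain no grade 1 events, so they are the same at every g.

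**The case against.** The best reply is that Section 7.8 sets a minimum. It does not bar grade 1 entries, and the toxicity form and its completion instructions are not in the documents. A reader might infer that the rates in Section 13.5 are certain to be biased down. The documents do not support that: the loss follows only if sites record the minimum and the tables are read as any-grade. One can also read Section 13.5 together with Section 7.8, so that each toxicity means each toxicity required to be reported. On that reading the numerator and interval are correct and only the label is loose. This stands as a limit on the claim. It does not remove the mismatch, because Section 13.5 does not say so and does name a floor in its next sentence.

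Four other inferences are tempting and should not be drawn.

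- That Section 13.7.2 counts patients with only grade 1 events as event-free. It says "Note that a patient who had no adverse events constitutes a safety assessment", which keeps such patients in the denominator and classifies no events.
- That Section 2.3 shows pembrolizumab events to be mostly low grade. It says most were not serious, and seriousness is not grade.
- That volunteered grade 1 reporting will differ by arm because the trial is open label. This is possible, but nothing in the documents points to it, and one office collects and quality-checks the data (Section 12.1.1).
- That the trial will look falsely safe against the earlier eribulin studies. The plan contains no historical comparison; it summarizes toxicity by arm with a concurrent randomized control.

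**Conclusion.** The conflict between the data rule and the analysis rule is real. If only the Section 7.8 minimum is recorded, the Section 13.5 tables understate any-grade incidence by the factor 1−g. If grade 1 events are volunteered in part, the tables mix two thresholds. The size cannot be computed from the documents because g is not given. The working shows a true 18% reported anywhere from 18% (g = 0) to 4.5% (g = 75%), and those endpoints are illustrations, not estimates.

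The consequence is confined to the descriptive safety tables. The grade 3+ comparison, the primary endpoint, the interim rule and all other efficacy analyses are untouched. The point is worth correcting because the correction costs almost nothing and makes each published rate interpretable.

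**What to change.** Change Section 13.5 so that its threshold matches Section 7.8. Suggested text: 'The incidence of each grade ≥2 toxicity will be reported by arm with a 95% exact CI. The maximum-grade table will use the categories none or grade 1, 2, 3, 4 and 5. Volunteered grade 1 records will be excluded from incidence rates.' The combined first category is needed because forms completed to the minimum cannot separate no event from grade 1. This is wording only, with no new data collection. Its cost is that the trial makes no any-grade claim.

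If any-grade rates are wanted, leave Section 13.5 as it is and change Section 7.8 to require grade 1 events on the toxicity forms. The cost is additional form entry for sites, and rates would be on a single threshold only for patients recorded under the new rule throughout.

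Section 13.7.2 needs no change under either option.

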## **13.6 Analysis of Correlative Science Endpoints**

All analyses of correlative scientific endpoints are exploratory and hypothesis-generating. Any promising findings will be tested in future studies.

### **13.6.1 *Blood and tissue correlative science endpoints:***

- We will describe the presence and abundance of multiple immune markers in metastatic HR-positive breast tumors (characterization will be based on histology, protein

expression, and mRNA expression; see Section 9 for further details on characterization) using frequency tables and descriptive statistics (mean, standard deviation, median, and inter-quartile range).

- We will explore the correlation of immunosuppressive and/or immune-stimulating immune marker profiles at baseline to disease response to therapy (response assessed by RECIST 1.1 and irRECIST criteria) using odds ratios and 95% confidence intervals.
- We will summarize serial changes in immune marker profile in peripheral blood mononuclear cells (PBMCs) from baseline (pre-trial therapy) using mean, standard deviation, median, and inter-quartile range.
- We will plot serial changes in the immunosuppressive and/or immune-stimulating immune marker profile in PBMCs by disease response to therapy (response assessed by RECIST 1.1 and irRECIST criteria)
- We will explore an immune marker or set of markers in circulating PBMCs that corresponds to tumor infiltrating lymphocyte (TIL) percentage in baseline tumor
- In the cohort of patients who have re-biopsy at progressive disease (PD): We will summarize changes in a broad array of immune markers from baseline to time of progressive disease on trial therapy using mean, standard deviation, median, and inter-quartile range.

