- 1.4.14 To explore whether the number and/or type of mutations identified using a next generation sequencing (NGS) panel is correlated with patient outcomes (PFS, ORR, CBR, and OS). This will be done on DFCI patients only.

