Kaufam et al examined the efficacy of eribulin vs. capecitabine among patients with metastatic breast cancer treated up to second line of chemotherapy. In this trial ORRs by independent review was 11.0% (95% CI, 8.5% to 13.9%) for the eribulin arm and the median PFS was 4.1 months (95% CI, 3.5 to 4.3 months) for eribulin.

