## **9.6 Hypothesis for correlative objectives**

### **9.6.1 Hypotheses**

- We hypothesize that the immune marker profile in the peripheral blood will change over the course of eribulin mesylate +/- pembrolizumab therapy.
- We hypothesize that a larger increase in markers of immune activity in the peripheral blood will correlate with a better disease response as assessed on concurrent restaging scans, and in terms of best radiographic response at any time on trial.  
We hypothesize that an immune marker or composite of markers in the peripheral blood at baseline will correspond to TIL percentage in archival tumor tissue.
- We hypothesize that the immune activity associated with a breast tumor, as assessed both in tumor tissue and in circulating blood, will be less at the time of disease progression on therapy compared to the time of therapy initiation.
- We hypothesize that the structure and function of the gut microbiome differs among patients with breast cancer.
- We hypothesize that the structure and function of the gut microbiome before starting pembrolizumab and eribulin can be predictive of efficacy of this therapy, with a greater microbial diversity, estimated by Shannon index, being predictive of efficacy.
- We hypothesize that the structure and function of gut microbiome changes in response pembrolizumab-based therapy and can predict the likelihood of response to pembrolizumab.
- We hypothesize that the abundance and functional profile of specific gut bacteria is associated with response to pembrolizumab.

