### **13.2 Sample Size, Accrual Rate and Study Duration**

The target accrual is 88 patients (44 in eribulin mesylate alone arm and 44 in eribulin mesylate+pembrolizumab combination arm). The study has 83% power to distinguish a 3 month improvement in PFS from 4.1 to 7.1 months (HR = 0.58) with a one-sided alpha of 0.1. This statement of power assumes a final analysis when 70 PFS events are observed, and would be anticipated to occur after a constant accrual over 18 months with 6 months of additional follow-up. Further assumptions are a constant hazard of PFS and dropout such that 5% of patients are lost-to-follow-up at 1 year. This allows for one futility analysis at 50% information (35 PFS

events) and would stop early if the Z-statistics from the logrank test is less than 0 (i.e. observed HR from a Cox model  $> 1.0$ ).

The expected accrual rate is 3-5 patients per month, and the accrual is expected to complete within 18-24 months.

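### Section 13.6.1 relates immune markers to response alone; adding best percent change in target diameters and PFS would use outcome data that the trial already collects

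*Combined protocol and SAP*

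**What the plan says.** Section 13.6.1 covers the blood and tissue markers. For baseline markers it states: "We will explore the correlation of immunosuppressive and/or immune-stimulating immune marker profiles at baseline to disease response to therapy", with response judged by RECIST 1.1 and irRECIST and summarized by odds ratios with 95% confidence intervals. Serial PBMC changes are to be plotted by response. Objectives 1.4.2 and 1.4.4 frame both questions as a contrast between patients with and without response. The PBMC hypothesis in Section 9.6.1 speaks of "a better disease response as assessed on concurrent restaging scans" and of best radiographic response.

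The other correlative strands are wider. Section 13.6.2 relates the microbiome to objective response and to PFS. Objective 1.4.14 asks whether tumor mutations are such that their number or type "is correlated with patient outcomes (PFS, ORR, CBR, and OS").

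Section 13.6 calls all correlative analyses exploratory. No responder count, marker effect size, alpha or power is stated for the immune markers.

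**The concern.** Section 2.6.1 describes immune-marker work as the bulk of the correlative science, yet it has the narrowest outcome of the three strands, and no reason is given.

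Response by RECIST is largely a cut of a continuous quantity that the trial already measures: change in the sum of target diameters (Section 11.1.3.1). When few patients respond, the cut discards much of the information. It also places stable disease of 27 weeks or longer, which Section 11.1.5 counts as clinical benefit, in the same group as progression at the first scan.

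Section 13.6 says that promising findings will be tested in later studies, so these analyses serve as a screen. A screen with wide intervals may fail to separate a useful marker from noise.

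**Working it through.** **1. The plan's own power figure.** None is given for the markers. The nearest is Section 13.2: "The study has 83% power to distinguish a 3 month improvement in PFS from 4.1 to 7.1 months (HR = 0.58"), one-sided alpha 0.1, with "a final analysis when 70 PFS events are observed". Schoenfeld's formula gives Φ(½·√70·ln(1/0.58) − 1.2816) = Φ(2.279 − 1.282) = 84.1%; Freedman's gives 82.7%. Allowing for the futility look at 35 events, which "would stop early if the Z-statistics from the logrank test is less than 0", Schoenfeld's becomes 82.6%. The stated 83% is reproduced.

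**2. Number of responders.** Section 13.2: "The target accrual is 88 patients". For the eribulin-versus-capecitabine trial, Section 2.4 says: "In this trial ORRs by independent review was 11.0"%. The highest eribulin rate quoted there is 21.3%.
- 88 × 0.110 = 9.7
- 88 × 0.213 = 18.7

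That is about 10 to 19. The 9.3% quoted for a more heavily pretreated population would give 8.2. All are eribulin-alone rates, and half the patients receive the combination.

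**3. Cost of the split against continuous size change.** These are assumptions, not document inputs: marker and tumor shrinkage are bivariate normal with correlation r; responders are the top fraction p; all 88 patients have both values; the test is two-sided at 5%.

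The split reduces r to r′ = r·φ(z)/√(p(1−p)), where z is the upper-p normal point.
- p = 0.11: 0.188/0.313 = 0.601, and 0.601² = 0.36, so about 36% of the information is kept.
- p = 0.20: 0.280/0.400 = 0.700, and 0.700² = 0.49, so about 49% is kept.

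Power by Fisher's z is Φ(atanh(r)·√(n−3) − 1.96). At r = 0.30, n = 88:
- continuous: Φ(0.3095 × 9.220 − 1.96) = Φ(0.894) = 0.814
- split, p = 0.11: r′ = 0.180, so Φ(0.1823 × 9.220 − 1.96) = Φ(−0.279) = 0.390

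| r | Continuous | Split, ORR 11% | Loss (points) | Split, ORR 20% | Loss (points) |
|---|---|---|---|---|---|
| 0.1 | 0.152 | 0.086 | 7 | 0.099 | 5 |
| 0.2 | 0.464 | 0.200 | 26 | 0.255 | 21 |
| 0.3 | 0.814 | 0.390 | 42 | 0.502 | 31 |
| 0.4 | 0.974 | 0.618 | 36 | 0.756 | 22 |
| 0.5 | 0.999 | 0.816 | 18 | 0.921 | 8 |

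Simulation with 10 and 18 responders agrees (81% against 39% and 51% at r = 0.3). At a response rate of 30% the loss is 21 to 24 points for r = 0.25 to 0.35. With fewer patients at r = 0.3, power is 0.65 against 0.28 or 0.36 (n = 60), and 0.51 against 0.21 or 0.28 (n = 44).

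**4. The same loss as interval width.** Section 13.6.1 does not say how the marker enters the odds ratio. Take a true odds ratio near 1.
- Median-split marker, 10 responders: SE = √(2/5 + 2/39) = 0.672, so the 95% limits lie a factor exp(1.96 × 0.672) = 3.7 either side. With 18 responders: √(2/9 + 2/35) = 0.529, factor 2.8.
- Continuous marker, per SD: SE = 1/√(88p(1−p)), which is 0.336 with 10 responders (factor 1.9) and 0.264 with 18 (factor 1.7).

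**5. PFS.** The result depends on an assumption that the documents do not supply.
- If the marker acts through shrinkage (r = 0.30; log hazard 0.5, 0.75 or 1.0 per SD of shrinkage; 70 events), simulated Cox power is about 0.20, 0.31 or 0.42. The response split has 0.39 to 0.50.
- If instead the hazard ratio per SD is as large as the odds ratio per SD, say 1.5, PFS power is Φ(√70 × 0.405 − 1.96) = 0.92. Response power is Φ(2.977 × 0.405 − 1.96) = 0.23 with 10 responders, where 2.977 = √(10 × 78/88).

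**The case against.** The strongest reply is that the analysis matches its objectives: 1.4.2 and 1.4.4 ask about patients with and without response, and odds ratios answer that. Section 13.6.1 plans estimates and plots, with no test, alpha or power target, so the two-sided 5% criterion is the reviewer's. The wide intervals will be visible to any reader. The correlation near 0.3 is assumed and lies close to where the loss is greatest.

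Each of these stands. They are why the odds ratios should stay, and why the loss is best read as imprecision and given as a range. They do not remove the benefit of adding outcomes, since the section's purpose is to find markers worth testing later.

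Further limits also stand:
- 88 is a ceiling. Eligibility requires an evaluable lesion (3.1.2), Section 11.1.1 provides for patients without measurable disease, baseline biopsy is optional, and missing archival tissue excludes no one (Section 9).
- The PBMC plots by response, and the wording of 9.6.1, leave room for ordered response categories and do not force a two-way split.
- The responder count carries eribulin-alone rates over to both arms.

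A reader might infer that PFS, with 70 planned events, must be far more powerful than a comparison resting on 10 to 19 responders. The documents do not support that: step 5 shows that PFS can do worse or better.

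**Conclusion.** The point holds as a low-cost improvement. The analyses in 13.6.1 that relate immune markers to outcome use response alone, unlike 13.6.2 and objective 1.4.14. That inconsistency rests on no assumed effect size.

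The size does rest on assumptions. With r between 0.2 and 0.4, markers in all 88 patients and a response rate of about 11% to 20%, the split loses about 20 to 40 points of power against continuous size change. The loss is about 5 to 7 points at r = 0.1 and 8 to 18 at r = 0.5, and it is smaller at higher response rates. The documents state neither r nor a combination response rate, so this is a range and not a prediction.

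Two stronger readings are not supported. One is that the loss applies equally against PFS; the case for PFS is consistency and coverage of patients without measurable disease, not a promised gain in power. The other is that the planned analysis is invalid; it answers its stated objectives, but imprecisely. The point concerns only the parts of 13.6.1 that relate markers to outcome; the rest is descriptive or relates PBMC markers to lymphocyte infiltration.

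**What to change.** Keep the responder odds ratios for objectives 1.4.2 and 1.4.4, and add to Section 13.6.1:

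- **Tumor size.** Spearman correlation or linear regression of the continuous marker with best percent change in the sum of target diameters, in patients with measurable disease.
- **PFS.** A Cox model with the continuous marker, adjusted for treatment arm, in all treated patients with marker data. Report any marker-by-arm interaction as exploratory. Without the arm term, treatment and prognostic effects would be mixed.
- **On-treatment PBMC change.** Blood is drawn every three weeks, so name one landmark sample in advance and start PFS at that sample, in patients still event-free and sampled then. Otherwise patients who stay on treatment longer contribute more change by design.

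The cost is a wording change and a few more models on data already collected; no visits, samples or patients are added. There are more exploratory estimates to report. Percent change is missing in patients without measurable disease, ignores new lesions, and does not correspond to irRECIST as defined in Section 11.3, which uses sums of products and includes new measurable lesions.
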